#### Serious adverse events (SAEs)

- i) Anaphylaxis (Immediate)
- ii) Pulmonary embolism or infarction (Immediate)
- iii) Outset of any neoplastic change (Late)
- iv) Outset of new Cardiovascular events (Late)
- v) Outset of new Cerebrovascular or neurological events (Late)
- vi) Reactivation of treated tuberculosis (Late)
- b) Change from baseline to 24 week visit in estimated glomerular filtration rate (eGFR) and split renal function in all patients for Phase II [Time Frame: Weeks 0, 24]
  - eGFR with split renal function will be evaluated using DTPA Renogram.
- c) Change from baseline to 24 week visit in estimated glomerular filtration rate (eGFR) with serum creatinine level in patients with CKD 4 and below for Phase II [Time Frame: Weeks 0, 2, 4, 12, 24]
  - eGFR will be calculated by Serum Creatinine level using MRDR formula during all visits.
- d) Change from baseline to 24 week visit in need for dialysis in patients with CKD 5 for phase II [Time Frame: Weeks 0, 2, 4, 12, 24]

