#### 4.8 Eligibility criteria

#### 4.8.1 Inclusion criteria

A patient is eligible for the study if all of the followings apply:

- a) Aged 18-80 years (inclusive)
- b) With chronic kidney disease (CKD)stage 3 to 5 (eGFR 60 to 0 mL/min/1.73m2 (inclusive)) Note: eGFR = estimated glomerular filtration rate
- c) Having provided informed written consent.

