#### Need for dialysis is described as

- i) No dialysis needed Score 0
- ii) Randomly (more than 6 days interval) Score 1
- iii) At 6 (six) days interval / Once weekly Score 2
- iv) At 5 (five) days interval Score 3
- v) At 4 (four) days interval Score 4

- vi) At 3 (three) days interval / 2 times a week Score 5
- vii) At 2 (two) days interval Score 6
- viii) At 1 (one) day interval / every alternate day./ 3 times a week Score 7

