#### **4.11.2 Secondary Outcome Measures**

a) Change from baseline to all post-treatment visits in body weight [Time Frame: Weeks 0, 2, 4, 12, 24, 36, 48]

Weight in Kg will be recorded for each patient during each follow up

b) Change from baseline to all post-treatment visits in Blood-pressure [Time Frame: Weeks 0, 2, 4, 12, 24, 36, 48]

Blood pressure will be measured in each patient during each follow up

- c) Change from baseline to all post-treatment visits in S.creatinine [Time Frame: Weeks 0, 2, 4, 12, 24, 36, 48]
  - a. S. Creatinine level will be measured during each follow up.
  - b. In case of patients having dialysis Pre and Post dialysis S. Creatinine levels will be measured at or near follow up dates.
- d) Change from baseline to all post-treatment visits in blood urea nitrogen (BUN) [Time Frame: Weeks 0, 2, 4, 12, 24, 36, 48]

Blood Urea Nitrogen will be measured in all patients during each follow up.

- e) Change from baseline to all post-treatment visits in Hemoglobin level [Time Frame: Weeks 0, 2, 4, 12, 24, 36, 48]
  - a. Hemoglobin level will be measured in gm/dl and percentage
  - b. Need for blood transfusion will be recorded
  - c. Need for erythropoietin will be recorded
- f) Change from baseline to all post-treatment visits in urine microalbumin-to-creatinine ratio (UMCR) [Time Frame: Weeks 0, 2, 4, 12, 24, 36, 48]

Urinary Microalbumin and creatinine will be measured in each patient during each follow up

g) Change from baseline to all post-treatment visits in hemoglobin A1c [Time Frame: Weeks 0, 2, 4, 12, 24, 36, 48]

HbA1C will be measured in each patient during each follow up

h) Change from baseline to all post-treatment visits in random blood sugar (RBS) [Time Frame: Weeks 0, 2, 4, 12, 24, 36, 48]

RBS will be measured in each patient during each follow up

i) Percentage of patients with hypoglycemia (defined as blood glucose < 55 mg/dL or 3.0 mmol/L) at all post-treatment visits [Time Frame: Weeks 0, 2, 4, 12, 24, 36, 48]

Patients will be asked if he or she had experienced any episode of hypoglycemia with clinical features of altered level of consciousness, sweating, nausea or vomiting with blood glucose < 55 mg/dL or 3.0 mmol/L

j) Change from baseline to all post-treatment visits in eGFR [Time Frame: Weeks 0, 2, 4, 12, 24, 36, 48]

eGFR will calculated using MDRD formula for each patient during each follow up

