#### **ANNEXURE - C**

#### **QUESTIONNAIRE - 1**

#### (CLINICAL ASSESSMENT - DURING ALL VISITS)

**PARTICULARS OF THE PATIENT: CODE NO:** NAME: AGE: SEX: M/F**HOSPITAL REG. NO:** PHONE: **ADDRESS: CONTACT PERSON:** PHONE: **DIAGNOSIS (Put Tick Mark Beside The Appropriate Selection):** 1) CKD: Stage 3A Stage 3B Stage 4 Stage 5 a) GN Need for dialysis Score b) IgA Nephropathy a) No dialysis yet 0 1 c) FSGS b) Occasional (> 6 days interval) d) Interstitial Nephritis c) At 6 (six) days interval / Once weekly 2 3 e) No Biopsy done d) At 5 (five) days interval e) At 4 (four) days interval 4 f) At 3 (three) days interval / 2 times a week 5 6 g) At 2 (two) days interval 7 h) At 1 (one) day interval / 3 times a week -2) HYPERTENSION 3) DM 4) Hypothyroidism 5) HYPERPARATHYROIDISM 6) IHD < NyHA Gr III or IV 7) CLD < Child Pugh C 8) CVD 9) OTHERS (if any) **SYMPTOMS (Put Tick Mark Beside The Appropriate Selection):** Better/Good/As usual/Bad/Worse **Urine output:** Scanty / Reduced / Normal **General Welbeing** Anorexia: Yes / No Convulsion: Yes / No Yes / No Loss of Consciousness: Yes / No Nausea: Vomiting: Yes / No Muscle spasm: Yes / No Hiccough: Yes / No Pain Yes / No Weakness: Yes / No **Fever** Yes / No Weight loss: Yes / No Yes / No Headache: Swelling of body: Yes / No **Respiratory distress:** Yes / No Vertigo: Yes / No Chest pain: Yes / No Constipation: Yes / No **Abdominal Pain:** Yes / No Loose motion: Yes / No Others (if any): **SIGNS: Body weight: Blood pressure:** Oedema:

35

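### Primary outcomes (c) and (d) are split by CKD stage, not dialysis status, so a stage 5 patient not on dialysis at week 0 falls outside (c) and enters (d) at a score that cannot improve

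*Combined protocol and SAP*

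**What the plan says.** Section 4.8.1 admits CKD stages 3 to 5, with eGFR from 60 down to 0. Dialysis is neither required nor excluded there or in section 4.8.2.

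Section 4.11.1 then sets three Phase II primary outcomes for kidney function, each as change from baseline to week 24:

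- (b) eGFR and split function by DTPA renogram, in all patients, at weeks 0 and 24.
- (c) "estimated glomerular filtration rate (eGFR) with serum creatinine level in patients with CKD 4 and below for Phase II".
- (d) "Change from baseline to 24 week visit in need for dialysis in patients with CKD 5 for phase II".

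The scale for (d) runs from "No dialysis needed Score 0" up to alternate-day dialysis, "3 times a week Score 7". Questionnaire 1 in Annexure C, completed at all visits, offers "No dialysis yet" as its zero option.

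Secondary outcome (j) in section 4.11.2 applies to everyone: "eGFR will calculated using MDRD formula for each patient during each follow up". Secondary outcome (c) asks for separate pre- and post-dialysis creatinine in dialysed patients.

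Section 4.15 names descriptive, univariate, multivariate and logistic methods in general terms. It does not say how (d) is summarised, and it has no rule for a stage 5 patient whose week-0 score is 0.

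**The concern.** The split between (c) and (d) works only if every stage 5 patient is on dialysis at week 0 and no one else is. The eligibility criteria do not ensure that.

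Where it fails, the patient is taken out of the primary creatinine-eGFR analysis and placed on a scale already at its floor. Specific objective (iii) is to see whether the treatment reverses or limits progression. In (d) such a patient cannot show reversal. Staying off dialysis, arguably a success for limiting progression, scores the same zero as a dialysed patient whose schedule did not change.

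At stake is what (d) means. Among dialysed patients it asks whether sessions become less frequent. Among the others it asks whether dialysis starts. One combined summary answers neither cleanly, and with 31 patients in total one or two dialysis starts could move it visibly.

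**Working it through.** **The plan's own figure.** Section 4.6 uses alpha 0.05 two-sided, beta 0.20, E = 0.5 and SD of change 1.0. N = (z for alpha + z for beta)² / (E/SD)² = 7.849 / 0.250 = 31.4, which the plan gives as 31. This is a one-sample calculation for a change. Normal-approximation power at n = 31 is Φ(0.5 × √31 − 1.960) = 79.5%. The calculation is not tied to (b), (c) or (d), or to the subsets used in (c) and (d).

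**Where each patient falls.** CKD 4 and below is read as stages 3 and 4, since (d) takes CKD 5.

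| Week-0 status | (b) DTPA eGFR | (c) creatinine eGFR | (d) dialysis score | Secondary (j) |
|---|---|---|---|---|
| Stage 3–4 | yes | yes | no | yes |
| Stage 5, on dialysis | yes | no | yes, from 1–7 | yes |
| Stage 5, not on dialysis | yes | no | yes, from 0 | yes |

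**Possible change in (d).** From week-0 score b, change lies between −b and 7 − b.

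- b = 0: 0 to +7. No change or worsening is possible; improvement is not.
- b = 7: −7 to 0. Worsening is not possible.

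**Illustration 1: a mean of (d).** Assume 12 stage 5 patients, 6 dialysed and 6 not, with every dialysed patient one step better (total −6).

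- Dialysed patients alone: −6/6 = −1.00.
- All 12, the others stable: −6/12 = −0.50.
- One start at score 5: (−6 + 5)/12 = −0.08.
- Two starts at score 1: (−6 + 2)/12 = −0.33.
- Two starts at score 5: (−6 + 10)/12 = +0.33.

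The sign reverses only if the starters' scores sum to more than 6.

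**Illustration 2: dilution of (d).** Assume 16 of 31 patients are stage 5. A share g is dialysed and improves by 0.5 with SD 1; the rest stay at 0. Mean = 0.5g, SD = √(g + 0.25g(1 − g)), power = Φ(√16 × mean/SD − 1.960).

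| Score 0 at week 0 | Standardised effect, all 16 | Power, all 16 | Power, dialysed only | n in (c) if split by dialysis status | Power in (c) at 0.5 SD |
|---|---|---|---|---|---|
| 0 | 0.50 | 52% | 52% | 15 | 49% |
| 4 | 0.42 | 39% | 41% | 19 | 59% |
| 8 | 0.33 | 27% | 29% | 23 | 67% |
| 12 | 0.23 | 15% | 17% | 27 | 74% |

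Separating the strata gains (d) only 2 to 3 percentage points of power.

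**Illustration 3: (c) by one-sample t.** Assume 19 patients in stages 3–4 and 6 undialysed stage 5 patients. Power at 0.5 SD, 5% two-sided, is 54.1% at n = 19 and 67.0% at n = 25. If adding the 6 lowers the pooled effect to 0.43 SD, power at n = 25 is 54% and the gain is gone.

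**The case against.** A reader might infer that these patients have no primary eGFR outcome. They do: (b) covers all patients by DTPA and can move in either direction, and (j) covers creatinine eGFR as a secondary outcome. They miss one of two primary eGFR outcomes. This objection stands and lowers the importance of the point.

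A reader might also infer that only worsening can be recorded at score 0. No change can be recorded too, and staying off dialysis bears on objective (iii). What cannot be recorded is improvement.

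It is tempting to say that the mean of (d) will mislead. The plan does not say that (d) is summarised by a mean, so the means above show what one pooled summary could do, not what the plan prescribes.

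The zero option on the form does not show that the sponsor expects undialysed stage 5 patients. The form serves stages 3 to 5 and needs a zero for stages 3 and 4 anyway. The support comes from eligibility, which permits such patients; there may be few or none.

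Finally, simply dropping score-0 patients from (d) would introduce a bias. Score-7 patients, who cannot worsen, would remain, and with no untreated control the outcome would tilt towards apparent benefit. Moving the score-0 patients into (c) also needs a rule for those who start dialysis before week 24. Both objections stand and shape the fix.

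None of this removes the floor in (d) or supplies the missing rule.

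**Conclusion.** The point holds in a limited form. As written, an eligible stage 5 patient not on dialysis at week 0 is outside (c) and enters (d) where improvement cannot be recorded. Any single summary of (d) would then combine two different questions. This follows from the outcome definitions and the eligibility criteria alone.

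The size is unknown, because the documents give neither the stage mix nor the number on dialysis. The illustrations rest on assumed mixes and effects. They show halving of a mean when half the stage 5 patients start at 0, and a sign reversal only under particular dialysis starts. A general power gain is not established: (d) gains little, and (c) gains only if the added patients respond similarly. The benefit of changing the definitions is mainly interpretability.

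**What to change.** - **Outcome (c):** define it as change in MDRD eGFR to week 24 in all patients not on dialysis at week 0 (score 0), whatever their stage. State how values after a dialysis start before week 24 are handled; for example, use the last pre-dialysis value, with a sensitivity analysis that counts a start as worsening.
- **Outcome (d):** keep all CKD 5 patients, reported in two strata by week-0 dialysis status. For score 1 or more, report improved, unchanged and worsened, and note that score-7 patients cannot worsen. For score 0, report the number starting dialysis by week 24 with an exact 95% CI, still as part of the primary outcome.
- **Overlap:** say that undialysed stage 5 patients contribute to both (c) and the second stratum of (d).

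The cost is revised wording for two outcomes and one handling rule. Week-0 dialysis score, creatinine and MDRD eGFR are already collected. The downside is smaller strata in (d) and wide intervals. With no starts among 6 patients, for example, the exact upper limit is 1 − 0.025^(1/6) = 46%.

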#### 4.2 Arms and Interventions

Arms: Participants having a harvested total "Adipose Derived Stem Cell (ADSC)" count (in 5 ml SVF solution) between 1 x 10^6 to 2 x 10^6 will be placed in "Group A".

Participants having a harvested total "Adipose Derived Stem Cell (ADSC)" count (in 5 ml SVF solution) more than  $2 \times 10^6$  will be placed in "Group B".

Interventions: Both group A and Group B will be injected intravenously with harvested 5 ml of SVF containing Autologous Non Expanded ADSC and outcome will be observed over the period of 1(one) year.

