#### 4.11 Outcome measures

#### **4.11.1 Primary Outcome Measure**

a) Incidence of minor adverse events (MAEs), serious adverse events (SAEs) which may be immediate, early or late - for Phase I [Time Frame: Week 48]

Minor adverse events (MAEs):

i) Pain from lipo-suction > 7 days (Early)

- ii) Fever > 7 days (Early)
- iii) Subcutaneous hematoma / abscess formation (Early)
- iv) Allergic reaction (Immediate)

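### No outcome counts patients who start dialysis from baseline CKD 3-4, or who start or increase it in any stage after week 24

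*Combined protocol and SAP*

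**What the plan says.** Stages 3 to 5 are eligible (section 4.8.1: "With chronic kidney disease (CKD)stage 3 to 5"), safety is specific objective (i) in section 3.2, and section 4.2 says "outcome will be observed over the period of 1(one) year".

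The renal and safety outcomes are these:

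- **Primary (a), Phase I, to week 48:** "Incidence of minor adverse events (MAEs), serious adverse events (SAEs) which may be immediate, early or late - for Phase I". Four minor and six serious events follow, and the last is "Reactivation of treated tuberculosis (Late"). There is no item for other events, no general definition of seriousness, and no statement that the list is either complete or illustrative.
- **Primary (b), Phase II:** change in DTPA GFR and split function from week 0 to week 24, in all patients.
- **Primary (c), Phase II:** change in creatinine-based eGFR to week 24, in CKD 4 and below.
- **Primary (d), Phase II:** "Change from baseline to 24 week visit in need for dialysis in patients with CKD 5 for phase II", assessed at weeks 0, 2, 4, 12 and 24. The score runs from 0 (none) to its top category, "At 1 (one) day interval / every alternate day./ 3 times a week Score 7".
- **Secondary (c), (d) and (j), section 4.11.2:** creatinine, BUN and eGFR to week 48, the last worded "Change from baseline to all post-treatment visits in eGFR". The only mention of dialysis among the secondary outcomes is a sampling instruction: "In case of patients having dialysis Pre and Post dialysis S. Creatinine levels will be measured at or near follow up dates".

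Questionnaire 1 in Annexure C is headed for use at all visits and carries both CKD stage and the dialysis score. Annexure D repeats the DTPA renogram at weeks 24 and 48. Section 4.15 (data analysis) does not mention dialysis.

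**The concern.** Starting dialysis, or needing it more often, is the clinical worsening that a CKD patient would most want reported. The protocol's own introduction argues for the treatment partly on the ground that it may spare patients dialysis. Yet the one dialysis outcome is limited to one stage and to the first half of follow-up, and it is a change in score rather than a number of patients.

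The gap is in what is counted, not in what is recorded. A reader of the final report could see mean changes in GFR and a list of named adverse events and still not learn how many of the infused patients began dialysis within the year, or went from weekly to three-times-weekly sessions after week 24.

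The laboratory outcomes do not fill the gap. Dialysis itself lowers creatinine, so a creatinine or eGFR change in a patient who has started dialysis depends on when the sample was taken. The protocol recognises this by asking for pre- and post-dialysis values, but it does not say which of them enters the eGFR formula.

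**Working it through.** The plan gives no figure on this point, so the check is a count of items and visits followed by worked cases on the protocol's own scale.

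**1. Named events in (a).** 4 minor + 6 serious = 10. Events concerning the kidney or dialysis: 0.

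**2. Visits covered by (d).** Post-baseline visits are at weeks 2, 4, 12, 24, 36 and 48, which is 6. Outcome (d) uses weeks 2, 4, 12 and 24, which is 4. Outside it: 6 − 4 = 2 visits (weeks 36 and 48), or 24 of the 48 weeks.

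**3. Gaps between visits.** 2, 2, 8, 12, 12 and 12 weeks. A short course of dialysis could fall between visits, so a score taken only on the day could miss it.

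**4. Worked cases.**

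| Patient | Score path | True rise | In (d) | Named event in (a) | Where else seen |
|---|---|---|---|---|---|
| Baseline CKD 5 | 2 at weeks 0 and 24, 7 at week 36 | 7 − 2 = 5 | change 2 − 2 = 0 | 0 | (b) to week 24; laboratory values to week 48 |
| Baseline CKD 4 | 0 at week 0, 7 by week 12 | 7 − 0 = 7 | not included if stage is fixed at baseline; could be included if stage is taken at the visit | 0 | (b) and (c), as a change in GFR |
| Baseline CKD 4 | 0 through week 24, 7 at week 36 | 7 − 0 = 7 | not captured on either reading | 0 | laboratory values to week 48 |

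A patient at score 7 at week 0 has a maximum possible rise of 7 − 7 = 0.

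**5. Scale, as an assumption only.** The planned size reproduces: 7.849 / 0.250 = 31.4, stated as 31. Suppose the 48-week risk of starting dialysis is r, with constant hazard, and all 31 patients are at risk. The probability of a start in weeks 24 to 48 is then √(1 − r) − (1 − r).

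- r = 0.05: 0.9747 − 0.95 = 0.0247; 31 × 0.0247 = 0.8 expected; chance of at least one 1 − (1 − 0.0247)^31 = 54%.
- r = 0.30: 0.8367 − 0.70 = 0.1367; 31 × 0.1367 = 4.2 expected; chance of at least one 99%.

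Neither value of r comes from the documents. Patients already dialysed at week 0 are not at risk of a start, so these figures are upper ones for each r. The conclusion does not depend on them.

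**The case against.** The strongest reply is that the protocol treats renal course as Phase II efficacy, not as Phase I safety, and assesses it well. Outcome (b) covers every stage at week 24, (c) covers stages 3 and 4 at each visit to week 24, and creatinine, BUN and eGFR continue to week 48. Dialysis is also part of the natural course of stages 3 to 5, and without a control it cannot be attributed to the infusion. **This largely stands.** It would be wrong to infer that worsening in stages 3 and 4 goes unassessed, or that dialysis must become a primary safety event. Counting every single session or one-point rise as primary harm would be debatable. But a change in GFR is still not a number of patients who began dialysis. The protocol does define a patient-level percentage elsewhere, for hypoglycaemia in secondary (i).

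A reader might also infer that the trial would report no serious adverse event in a patient who began dialysis. That requires the ten items to be a closed list, which the text does not say. The missing general definition of seriousness is a wider matter, and dialysis is one instance of it.

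Secondary (c) asks for pre- and post-dialysis creatinine, so patients on dialysis would be partly visible to week 48. This helps, but it gives neither frequency nor starts.

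Finally, CKD 5 in (d) could mean stage at the visit, since Questionnaire 1 records stage each time. Some stage 4 starts by week 24 would then enter (d). The gap after week 24 remains.

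**Conclusion.** The concern holds as a gap in what is counted. Need for dialysis is an outcome only for CKD 5 and only to week 24; 0 of the 10 named safety events are renal; and 2 of 6 post-baseline visits have no dialysis outcome. The part about starts from stages 3 and 4 up to week 24 assumes that CKD 5 means baseline stage. The part about any stage after week 24 holds on both readings.

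The documents do not support saying that renal worsening is ignored, or that the safety report must come out clean. They also give no stage mix or dialysis rate from which to estimate how many patients are affected. The matter should be corrected because the remedy is small and the restriction in (d), followed as written, gives a change of 0 to a patient whose score rises by 5 at week 36.

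**What to change.** Keep (d) and state that CKD 5 in it means baseline stage. Add a secondary outcome, reported beside (a), for all infused patients of every baseline stage through week 48:

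1. **Starts:** the number with score 0 at week 0 and then 1 or more at a later visit, or dialysis reported since the last visit. List single or temporary sessions separately from continuing dialysis.
2. **Increases:** among those dialysed at week 0, the number with a higher score at weeks 24, 36 and 48. Give the number already at score 7, who cannot register a rise.

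State that the Questionnaire 1 score is completed for all stages at all visits, and add a question on dialysis since the last visit. Report n/N with exact 95% confidence intervals, overall and by baseline stage, and show deaths, transplants and the number reaching week 48. Flag eGFR and creatinine values taken after dialysis starts.

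**Cost:** protocol wording, one question per visit and one table. The form's layout, as it survives in the text, does not show whether the score box is meant for stage 5 only. If it is, add one tick per visit for stages 3 and 4. Some counted events will be natural progression, so the report should say that they cannot be attributed to SVF without a control.

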#### Need for dialysis is described as

- i) No dialysis needed Score 0
- ii) Randomly (more than 6 days interval) Score 1
- iii) At 6 (six) days interval / Once weekly Score 2
- iv) At 5 (five) days interval Score 3
- v) At 4 (four) days interval Score 4

- vi) At 3 (three) days interval / 2 times a week Score 5
- vii) At 2 (two) days interval Score 6
- viii) At 1 (one) day interval / every alternate day./ 3 times a week Score 7

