#### 2. Introduction

#### 2.1 Chronic Kidney Disease (CKD)

CKD is a disease of alarmingly increasing prevalence (8 to 16%) associated with mortality [1]. CKD can progress towards end-stage renal disease (ESRD), requiring renal replacement therapy. ESRD currently accounts for 6.3% of the medicare spending in the United States, and is projected to increase by 85% by 2015 [2]. In a study conducted among rural population in Bangladesh overall CKD prevalence was found about 19% [3]. Furthermore, ESRD has a major impact on quality of life and life expectancy [4]. Therefore, it is very important to develop therapeutic interventions to prevent, alleviate, or decelerate progression of renal failure.

Diabetes mellitus and hypertension represent major causes of CKD and initiation of dialysis [5]. In addition, glomerular diseases, malnutrition, infectious diseases, and acute kidney injury can progress to ESRD, contributing to the increased global burden of death [6]. Current treatment modalities often fail to target the major underlying contributors for progression of renal disease [7]. Management of CKD at present mostly aims at control of the predisposing factors and supplementation of kidneys homeostatic functions but not at the treatment of the diseased kidney itself. Again due to lack of adequate facilities or financial constraints people of a developing country like Bangladesh are unable to continue long term or lifelong dialysis. Chronic glomerular and tubule-interstitial fibrosis is a common pathway to ESRD, often associated with apoptosis, oxidative damage, fibrosis and microvascular rarefaction. Unfortunately, the regenerative potential of kidney is limited under chronic conditions and inefficient to prevent progressive glomerulosclerosis and tubule-interstitial fibrosis [8]. Treatment strategies that boost cellular regeneration might therefore offer good alternatives for patients with CKD.

In the western world as well as in Bangladesh, high blood pressure and type II diabetes are on the rise and are contributing to higher rates of kidney disease. Demand for kidney transplants is increasing. But there are not enough donor organs to meet this growing need. So, cell based therapies may offer an alternative solution.

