#### 4.9 Treatment allocation

All subjects would be submitted for Stromal Vascular Fraction (Autologous Adipose Derived Mesenchymal Stem Cell) Based Treatment for Chronic Kidney Disease

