#### 4.15 Data analysis

The edited data will then be entered on to the template of SPSS® 16 and STATA® 10/IC.

For Back ground variables and socio-demographic data descriptive statistics and relative frequency (percentage) will be generated.

Through univariate analysis the base line characteristics and treatment outcome will be compared. The effect of treatment will be identified through Multivariate analysis after adjusting for possible confounders. Relative risk with 95% CI will be generated through binary logistic regression adjusting for all possible confounders.

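### Primary outcome (d) does not separate needing dialysis from receiving it, and has no rule for transplant, cost-driven reduction or death

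*Combined protocol and SAP*

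**What the plan says.** Section 4.11.1(d) defines the outcome as "Change from baseline to 24 week visit in need for dialysis in patients with CKD 5 for phase II". The scale runs from 0 to 7. Score 0 is "No dialysis needed Score 0". Scores 1 to 7 are spacings between sessions, for example "At 3 (three) days interval / 2 times a week Score 5". The form completed at every visit (Annexure C, Questionnaire 1) labels score 0 differently, as "No dialysis yet". It has no dedicated field for why a schedule changed and none for a kidney transplant.

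The background (section 2.1) says that through lack of facilities or "financial constraints people of a developing country like Bangladesh are unable to continue long term or lifelong dialysis". On transplantation it says: "Demand for kidney transplants is increasing. But there are not enough donor organs to meet this growing need".

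On analysis, section 4.15 offers "The effect of treatment will be identified through Multivariate analysis after adjusting for possible confounders". It does not say what happens to a score after a transplant, after dialysis is cut for reasons other than kidney function, or when the week 24 score is missing. Section 4.9 states that "All subjects would be submitted for Stromal Vascular Fraction"; the two groups differ only in harvested cell count (section 4.1).

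**The concern.** The name of the outcome promises a measure of kidney function, but the grades record a treatment schedule. Schedules also change because a patient receives a donor kidney, runs out of money, loses access or chooses to attend less often. On this scale all of those move the score downward, which is the direction of benefit.

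Outcome (d) is the only Phase II primary specific to CKD 5. It bears directly on the objective of learning whether SVF can halt or turn back the disease, and avoiding dialysis is central to the rationale in section 2.9. With every participant treated, no comparison group would show the same drift. If the reason for a change is not recorded at the visit, it may not be recoverable at analysis.

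**Working it through.** **1. What the definition allows.** Take three CKD 5 patients on twice-weekly dialysis (score 5 at baseline), none of whom gains native kidney function.

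| Event before week 24 | Section 4.11.1(d) | Questionnaire 1 | Change |
|---|---|---|---|
| Transplant | Score 0 is literally true | Score 0 label does not fit someone who has already had dialysis | −5 if coded 0 |
| Cut to once weekly for cost | Score 2 fits exactly | Score 2 fits exactly | −3 |
| Stops for cost | Score 0 if read as sessions received; no valid level if read as need | Score 0 label does not fit | −5, or undefined |

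A patient who dies before week 24 has no score at that visit, and neither section 4.11.1 nor section 4.15 says what then happens. Death is also not among the serious adverse events named in section 4.11.1.

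**2. The plan's own figure.** Section 4.6 gives N = (1.960 + 0.842)² / (0.5/1.0)² = 7.85/0.25 = 31.4, stated as about 31. This reproduces. It does not bear on how (d) is defined and serves here only as the upper limit on the number of CKD 5 patients, which the protocol does not state.

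**3. Size of one misclassified patient.** Shift in mean change = (change in score)/n, with n the assumed number of CKD 5 patients.

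| Event | n = 10 | n = 20 | n = 31 |
|---|---|---|---|
| 5 to 0 | −5/10 = −0.50 | −5/20 = −0.25 | −5/31 = −0.16 |
| 7 to 0 | −7/10 = −0.70 | −7/20 = −0.35 | −7/31 = −0.23 |
| 5 to 2 | −3/10 = −0.30 | −3/20 = −0.15 | −3/31 = −0.10 |
| 0 to 5 (starts dialysis) | +0.50 | +0.25 | +0.16 |

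The last row matters. Eligibility reaches eGFR 0 without requiring dialysis (section 4.8.1), so some CKD 5 patients may enter at 0 and can only worsen. One of them starting dialysis at score 5 cancels one 5-to-0 move.

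**4. False-positive illustration (all inputs assumed).** The simulation assumes no true effect and a baseline of 5 or 7. A given share of patients drops to 0 for non-renal reasons, and the rest change by −1, 0 or +1 with probabilities 0.25, 0.50 and 0.25. The test is a one-sample t test, two-sided at 0.05, for which the nominal rate of significant improvement is 2.5%.

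| Share dropping to 0 | n = 10 | n = 20 | n = 31 |
|---|---|---|---|
| 10% | 3% | 12% | 31% |
| 20% | 11% | 49% | 79% |

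No patient enters at 0 and starts dialysis in this model, so the rates are high if that happens. The documents give no share for any of these events.

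**The case against.** The strongest reply is that the outcome is worded as need. Read literally, a patient who still needs dialysis but cannot pay does not qualify for score 0. That is fair for stopping because of cost, though the patient is then left with no valid level. It does not help with transplant, where score 0 is literally true, or with a cut to once weekly, where score 2 fits exactly.

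Other data would help. Outcome (b) measures renogram GFR in all patients, CKD 5 included. Pre- and post-dialysis creatinine is planned (section 4.11.2). Questionnaire 1 has space for other remarks, and section 4.12 plans a checklist of hospital records. A transplant would probably come to light. But nothing requires the reason for a schedule change to be recorded, or says how it would enter the analysis of (d).

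A reader might infer more than the documents support:

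- **That the protocol calls stopping for cost common.** Section 2.1 makes a general statement about long-term dialysis. It gives no rate, does not address a 24-week window, and describes donor organs as scarce.
- **That such patients are counted by rule as SVF successes.** No success threshold exists. The fault is a missing rule.
- **That every bias favours SVF.** Starting dialysis, or needing it more often, moves the score the other way. Even for deaths, dropping them is an assumption, because the analysis section is silent.
- **That the artefact matches the planned effect.** Twelve patients with changes of −5, −5, −3 and nine zeros give a mean of −13/12 = −1.08, SD 2.02, ratio 0.54, which looks comparable with E = 0.5. But section 4.6 does not tie E to outcome (d), and the inputs are chosen. Replacing one zero with a patient who starts dialysis (+5) cuts the ratio to 0.25, and replacing two cuts it to 0.08.

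**Conclusion.** The concern holds as a gap in the definition of a primary outcome. Need has no criterion apart from the schedule, the two score 0 labels disagree, and foreseeable events that imitate benefit have no handling rule and no field to identify them. It goes beyond missing detail because the scale as written accommodates a transplant and a cost-driven cut as improvement.

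A single such patient can move the mean change by roughly 0.1 to 0.7 points, depending on the starting score, the size of the drop and whether there are 10 or 31 CKD 5 patients. How many such patients there will be, and whether patients starting dialysis outweigh them, cannot be determined from the documents. The conclusion is therefore that a change in (d) could not be interpreted reliably, not that it must be biased toward SVF.

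**What to change.** 1. Reconcile the score 0 labels in section 4.11.1(d) and Questionnaire 1, so that one definition also covers a patient who has had dialysis and no longer receives it.
2. Add to Questionnaire 1 a reason for any change in dialysis schedule (kidney function, cost or access, patient choice, transplant, other) and a transplant date.
3. State in 4.11.1(d) that a reduction due to transplant, cost, access or choice is not counted as improvement. Report these events and deaths separately by category, and add a sensitivity analysis that assigns them an unfavourable score fixed in advance.
4. Show each reduction beside the creatinine, BUN, potassium and urine output already collected. Only creatinine is specified as pre- and post-dialysis, so record the timing of the others relative to a session.
5. Do not count eGFR values after a transplant as native-kidney improvement in primary outcomes (b) and (c) or secondary outcome (j).

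The cost is two form fields and a few sentences, with no new visits or tests. The observed improvement may be smaller. The fields should be in place before further visits take place, since reasons reconstructed later will be less reliable.
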